## **7.0 TRIAL PROCEDURES**

### **7.1 Trial Procedures**

The Trial Flow Chart - Section 6.0 summarizes the trial procedures to be performed at each visit. Individual trial procedures are described in detail below. It may be necessary to perform these procedures at unscheduled time points if deemed clinically necessary by the investigator.

Furthermore, additional evaluations/testing may be deemed necessary by the Sponsor and/or Merck for reasons related to subject safety. In some cases, such evaluation/testing may be potentially sensitive in nature (e.g., HIV, Hepatitis C, etc.), and thus local regulations may require that additional informed consent be obtained from the subject. In these cases, such evaluations/testing will be performed in accordance with those regulations.

#### **7.1.1 Administrative Procedures**

##### **7.1.1.1 Informed Consent**

The Investigator or clinical coordinator must obtain documented consent from each potential subject prior to participating in a clinical trial.

###### **7.1.1.1.1 General Informed Consent**

Consent must be documented by the subject's dated signature or by the subject's legally acceptable representative's dated signature on a consent form along with the dated signature of the person conducting the consent discussion.

A copy of the signed and dated consent form should be given to the subject before participation in the trial.

The initial informed consent form, any subsequent revised written informed consent form and any written information provided to the subject must receive the IRB/ERC's approval/favorable opinion in advance of use. The subject or his/her legally acceptable representative should be informed in a timely manner if new information becomes available that may be relevant to the subject's willingness to continue participation in the trial. The communication of this information will be provided and documented via a revised consent form or addendum to the original consent form that captures the subject's dated signature or by the subject's legally acceptable representative's dated signature.

Specifics about a trial and the trial population will be added to the consent form template at the protocol level.

The informed consent will adhere to IRB/ERC requirements, applicable laws and regulations and Sponsor requirements.

### **7.1.1.2 Inclusion/Exclusion Criteria**

All inclusion and exclusion criteria will be reviewed by the investigator or qualified designee to ensure that the subject qualifies for the trial.

### **7.1.1.3 Medical History**

A medical history will be obtained by the investigator or qualified designee. Medical history will include all active conditions, and any condition diagnosed within the prior 10 years that are considered to be clinically significant by the Investigator. Details regarding the disease for which the subject has enrolled in this study will be recorded separately and not listed as medical history.

### **7.1.1.4 Prior and Concomitant Medications Review**

#### **7.1.1.4.1 Prior Medications**

The investigator or qualified designee will review prior medication use, including any protocol-specified washout requirement, and record prior medication taken by the subject within 28 days before starting the trial. Treatment for the disease for which the subject has enrolled in this study will be recorded separately and not listed as a prior medication.

#### **7.1.1.4.2 Concomitant Medications**

The investigator or qualified designee will record medication, if any, taken by the subject during the trial. All medications related to reportable SAEs and ECIs should be recorded as defined in Section 7.2.

### **7.1.1.5 Disease Details and Treatments**

#### **7.1.1.5.1 Disease Details**

The investigator or qualified designee will obtain prior and current details regarding disease status.

#### **7.1.1.5.2 Prior Treatment Details**

The investigator or qualified designee will review all prior cancer treatments including systemic treatments, radiation and surgeries.

#### **7.1.1.5.3 Subsequent Anti-Cancer Therapy Status**

The investigator or qualified designee will review all new anti-neoplastic therapy initiated after the last dose of trial treatment. If a subject initiates a new anti-cancer therapy within 30 days after the last dose of trial treatment, the 30 day Safety Follow-up visit must occur before the first dose of the new therapy. Once new anti-cancer therapy has been initiated

the subject will move into survival follow-up.

#### **7.1.1.6 Assignment of Screening/Study Number**

All consented subjects will be given a unique screening number that will be used to identify the subject for all procedures that occur prior to allocation. Each subject will be assigned only one screening number. Screening numbers must not be re-used for different subjects. UCCC will be responsible for assigning screening numbers.

Any subject who is screened multiple times will retain the original screening number assigned at the initial screening visit. The screening number will be their study number as well once they are allocated to treatment.

#### **7.1.1.7 Trial Compliance**

Interruptions from the protocol specified treatment plan for greater than 3 weeks delay of Pembrolizumab doses, greater than five day delay for radiation treatment or more than 2 skipped doses for Cisplatin treatment require consultation between the investigator and the Sponsor and written documentation of the collaborative decision on subject management.

Administration of trial medication will be witnessed by the investigator and/or trial staff. The total volume of Pembrolizumab infused will be compared to the total volume prepared to determine compliance with each dose of Pembrolizumab administered. The instructions for preparing and administering Pembrolizumab will be provided in the Pharmacy Manual. Treatment with standard therapies will be prepared and administered as per the approved product label.

### **7.1.2 Clinical Procedures/Assessments**

#### **7.1.2.1 Adverse Event (AE) Monitoring**

The investigator or qualified designee will assess each subject to evaluate for potential new or worsening AEs as specified in the Trial Flow Chart and more frequently if clinically indicated. Adverse experiences will be graded and recorded throughout the study and during the follow-up period according to NCI CTCAE Version 4.0 (see Section 11.2). Toxicities will be characterized in terms regarding seriousness, causality, toxicity grading, and action taken with regard to trial treatment.

For subjects receiving treatment with Pembrolizumab all AEs of unknown etiology associated with Pembrolizumab exposure should be evaluated to determine if it is possibly an event of clinical interest (ECI) of a potentially immunologic etiology (termed immune-related adverse events, or irAEs).

Please refer to section 7.2 for detailed information regarding the assessment and recording

of AEs.

#### **7.1.2.2 Full Physical Exam**

The investigator or qualified designee will perform a full physical exam during the screening period. Clinically significant abnormal findings should be recorded as medical history. Full physical exam only includes full head and neck and fiberoptic exam at week 19 but can be completed between week 11 and 20 to count towards week 19 assessment.

#### **7.1.2.3 Directed Physical Exam**

For cycles that do not require a full physical exam per the Trial Flow Chart, the investigator or qualified designee will perform a directed physical exam as clinically indicated prior to trial treatment administration at each visit, and at any safety follow-up visits.

#### **7.1.2.4 Vital Signs**

The investigator or qualified designee will take vital signs at screening, prior to the administration of each dose of trial treatment and at treatment discontinuation as specified in the Trial Flow Chart (Section 6.0). Vital signs should include temperature, pulse, respiratory rate, weight and blood pressure. Height will be measured at screening only.

#### **7.1.2.5 Eastern Cooperative Oncology Group (ECOG) Performance Scale**

The investigator or qualified designee will assess ECOG status (see Section 11.1) at screening, prior to the administration of each dose of trial treatment and discontinuation of trial treatment as specified in the Trial Flow Chart.

#### **7.1.2.6 Tumor Imaging and Assessment of Disease**

Imaging will be performed at independent sites and the assessment of response will be determined by independent site investigators.

##### **7.1.2.6.1 Initial Tumor Imaging**

Prior to resection all patients should preferably undergo PET/CT and CT neck with contrast. However, chest CT with or without contrast in addition to CT neck with contrast is acceptable.

Scans performed as part of routine clinical management are acceptable for use as the screening scan if they are of diagnostic quality and performed within 42 days prior to the first dose of trial treatment.

##### **7.1.2.6.2 Post-Treatment Assessment Imaging**

Twelve weeks (+/- 2 weeks) after completion of last radiation treatment (week 19 on flow chart), a PET/CT or CT of neck and chest should be performed to assess for early relapse. Patients will be followed clinically for recurrence after initial post-treatment imaging. No

further imaging is required after initial assessment unless there is suspicion of relapsed disease.

#### **7.1.2.6.3 Assessment of Disease**

Patients will be assessed for response 12 weeks after completion of radiation. A full physical exam including head and neck and fiberoptic exam should be performed if indicated per standard of care but not required per protocol every 12 weeks for first 2 years following CRT and then at least every 24 weeks for the next 3 years. For patients felt to have a relapse at any time, a thorough ENT exam as well as a repeat biopsy is recommended to confirm relapsed disease. Follow-up imaging in 4-8 weeks is also acceptable if biopsy is not yet felt to be necessary or is non-diagnostic. Patients will be followed clinically every three months and any concern for relapsed disease or progression should trigger either imaging or biopsy for confirmation. Patients will be followed for relapse for a total of 5 years.

#### **7.1.2.7 Tumor Tissue Collection and Correlative Studies Blood Sampling**

Any subjects with oropharyngeal cancers must have documented HPV status (either by p16 or *in situ*).

##### **Biopsy tissue:**

For UC and all Sub-sites: Either a newly obtained core or archival biopsy tissue must be submitted (or determined available and sent at earliest convenience) prior to neoadjuvant Pembrolizumab dose.

For UC only: A biopsy block will be reviewed by the study pathologist ([name]) and retained in the histopathology core. All requests for tissues will be performed per study manual.

For all Sub-sites: Biopsy tissue should be submitted ideally as a block (preferred), or as 25 FFPE slides and 5 tissue scrolls.

For MDA only: Patients, including those with available archival tissue, will have a mandatory fresh biopsy at enrollment. Fresh tissue from biopsy will be processed by the [name] laboratory using normal procedures for single cell RNA sequencing.

##### **Resection tissue:**

For UC only: A resection block will be identified by the study pathologist ([name]) and retained in the histopathology core. All requests for tissues will be performed per study manual. Additional fresh tissue from resection should be collected and submitted per lab manual instructions. Fresh tissue will be prepared and cut by UC Pathology and/or Head and Neck Surgical Team (at least 500mg [0.5cm^3] but if feasible, 2gm [2cm^3] is preferable).

**For all Sub-sites:** Resection tissue should be submitted as a block (preferred), or as 25 FFPE slides and 5 tissue scrolls from all sub-sites.

**For MDA only:** Fresh tissue from resection will also be collected. Fresh tissue from resection collected from MDA will be processed by the [name] laboratory using normal procedures for single cell RNA sequencing.

Blood samples will be collected pre-dose of pre-surgical Pembrolizumab, immediately prior to resection, pre-dose first adjuvant Pembrolizumab dose and on adjuvant week 3 pre-dose of Cisplatin.

Detailed processing, shipping and handling will be provided in the procedures manual.

### 7.1.3 Laboratory Procedures/Assessments

Details regarding specific laboratory procedures/assessments to be performed in this trial are provided below.

#### 7.1.3.1 Laboratory Safety Evaluations (Hematology, Chemistry and Urinalysis)

Laboratory tests for hematology, chemistry, urinalysis, and others are specified in Table 5.

**Table 5 Laboratory Tests**

Hematology	Chemistry	Urinalysis	Other
Hematocrit	Albumin	Blood	Serum $\beta$ -human chorionic gonadotropin†
Hemoglobin	Alkaline phosphatase	Glucose	( $\beta$ -hCG)†
Platelet count	Alanine aminotransferase (ALT)	Protein	Total triiodothyronine (T3)
WBC (total and differential)	Aspartate aminotransferase (AST)	Specific gravity	Free tyroxine (T4)
Red Blood Cell Count	Lactate dehydrogenase (LDH)	Microscopic exam (if abnormal)	Thyroid stimulating hormone (TSH)
Absolute Neutrophil Count	Carbon Dioxide ‡	results are noted	
Absolute Lymphocyte Count	( $O_2$ or bicarbonate)	Urine pregnancy test †	Prothrombin time PT/INR

	Uric Acid		Partial Thromboplastin Time (PTT)
	Calcium		
	Chloride		Blood for correlative studies
	Glucose		
	Phosphorus		
	Potassium		
	Sodium		
	Creatinine		
	Magnesium		
	Total Bilirubin		
	Direct Bilirubin ( If total bilirubin is elevated above the upper limit of normal )		
	Total protein		
	Blood Urea Nitrogen		

† Perform on women of childbearing potential only. If urine pregnancy results cannot be confirmed as negative, a serum pregnancy test will be required.

‡ If considered standard of care in your region.

Laboratory tests for screening should be performed within 10 days prior to the first dose of treatment. After Cycle 1, pre-dose laboratory procedures can be conducted up to 72 hours prior to dosing. Results must be reviewed by the investigator or qualified designee and found to be acceptable prior to each dose of trial treatment.

### 7.1.3.2 Pharmacodynamic Evaluations

#### 7.1.3.2.1 Peripheral Blood Monocyte Cell (PBMC) Isolation

40 mls of whole blood will be collected in purple top EDTA tubes at 4 timepoints prior to Pembrolizumab administration (on day -28-6 before resection), on day of resection (day 0), prior to Pembrolizumab administration on adjuvant week 1, before 2nd chemotherapy (Cisplatin) and radiation on week 3 (see study calendar) and transferred at room temperature within 24 hours to UCCC.

PBMCs and plasma will be separated by Ficoll centrifugation at UCCC. Plasma will be frozen and stored at -80°C. PBMCs will be either cryopreserved or immediately processed for flow cytometry and functional analysis. Stored plasma will be used for cytokine assays. Please see procedure manual for full details.

### **7.1.3.2.2 Immunohistochemistry/Immunofluorescence/RNA In Situ Hybridization**

Archived biopsy and resected tissue and if fresh resected tissue (Cincinnati only) will be shipped to University of Cincinnati for analysis. FFPE and Frozen sections will be used to analyze the immune cell phenotype (markers include but are not limited to CD4, CD8, PD-1, FOXP3, A2aR, PD-L1, CD73).

### **7.1.3.2.3 Genomic Analysis**

When sufficient tissue is available, FFPE sections may be analyzed by RNA Sequencing and/or next generation whole exome sequencing to understand change in molecular pathways and/or prognostic genetic modifications as well as potential predictors of treatment response. At MDA, fresh biopsy and resection tissue will be used for single cell RNA seq analysis.

## **7.1.4 Other Procedures**

### **7.1.4.1 Withdrawal/Discontinuation**

When a subject discontinues/withdraws prior to trial completion, all applicable activities scheduled for the final trial visit should be performed at the time of discontinuation. Any adverse events which are present at the time of discontinuation/withdrawal should be followed in accordance with the safety requirements outlined in Section 7.2 - Assessing and Recording Adverse Events.

## **7.1.5 Visit Requirements**

Visit requirements are outlined in Section 6.0 - Trial Flow Chart. Specific procedure-related details are provided above in Section 7.1 - Trial Procedures.

### **7.1.5.1 Screening**

Potential subjects will be evaluated to determine that they fulfill the entry requirements as set forth in Section 5.1. Visit requirements are outlined in Section 6.0 – Trial Flow Chart. Results of a test performed prior to the subject signing consent as part of routine clinical management are acceptable in lieu of a screening test if performed within the specified time frame. Screening procedures are to be completed within 28 days prior to the first dose trial treatment except for the following:

- Laboratory tests and ECOG PS are to be performed within 10 days prior to the first dose of trial treatment.
- For women of reproductive potential, a serum pregnancy test will be

performed within 72 hours prior to the first dose of trial treatment. A urine test may be considered if serum test is not appropriate.

- Archival or newly obtained tumor collection is required to be obtained within 28 days prior to the first dose of trial treatment.

Subjects may be rescreened after initially failing to meet the inclusion/exclusion criteria and they have not yet started treatment, however, re-screening tests will not be covered by study. Results from assessments performed during the initial screening period are acceptable in lieu of a repeat screening test if performed within the specified time frame and the inclusion/exclusion criteria is met.

#### **7.1.5.2 Treatment Period**

Visit requirements are outlined in Section 6.0 – Trial Flow Chart. Specific procedure-related details are provided above in Section 7.1 – Trial Procedures.

#### **7.1.5.3 Post-Treatment Visits**

##### **7.1.5.3.1 Safety Follow-Up Visit**

If subjects do not discontinue or withdraw early:

- The mandatory Safety Follow-up Visit should correspond to approximately a week after the post-treatment imaging (week 19) on week 20's End of Treatment/Discontinuation visit.

If subjects discontinue or withdraw early:

- The mandatory Safety Follow-Up Visit should be conducted approximately 30 days after the last dose of trial treatment or before the initiation of a new anti-cancer treatment, whichever comes first.

For all subjects, all AEs that occur prior to the Safety Follow-Up Visit should be recorded. Subjects with an AE of Grade > 1 will be followed until the resolution of the AE to Grade 0-1 or until the beginning of a new anti-neoplastic therapy, whichever occurs first. SAEs that occur within 90 days of the end of treatment or before initiation of a new anti-cancer treatment should also be followed and recorded.

#### **7.1.5.4 Follow-up Visits**

Subjects will receive the follow-up PET/CT or CTs as outlined in flowchart in section 6.0. If subjects have no detectable relapse, they will complete the week 20 Safety Follow-up Visit (End of Treatment), and then they will move into the follow-up (post-treatment) stage of the study. Subjects will have follow-up visits every 3 months (12 weeks) either in person at a doctor visit or by phone (if being seen by outside oncologist) for the first 2 years and then every 6 months (24 weeks) for the next 3 years to monitor for relapse, or until time of

withdrawal of consent, or death, whichever comes first. Phone calls are an acceptable form of follow up for all subjects regardless if they are in the care of a local or outside oncologist. If subjects develop a relapse, they will continue to be followed at the time-points described in the flowchart in section 6.0. Every effort should be made to confirm relapse if suspected. During the follow up period, the follow up and survival follow up visits can be calculated in months rather than weeks in order to avoid potential protocol deviations with the scheduling window.

If patients have relapsed disease at time of post-treatment imaging, they should have follow-up imaging at discretion of investigator and, in addition to mandated 30-day safety follow-up, move into survival follow-up.

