Scheduling Window (Days):	-35 to -7	-22 to -7	-21 to -7	0	28 to 77	± 1	± 1	± 1	± 1	± 1	± 1	± 3	± 3	± 3	± 14	At time of Discon c	30 days and 3 months post discon	+/- 2 weeks
Adjuvant Treatment (Week):					1	2	3	4	5	6	7	10	13	16	19	(20 d )	20 d	

a. Patients will be followed every 3 weeks for first 3 months following CRT (post CRT above) and then every 3 months (every 12 weeks) for first 2 years followed by every 6 months (24 weeks) for a total of 5 years. Adjuvant weeks are numbered starting with first Pembrolizumab infusion which should begin 4-11 weeks after resection. FU visits can be conducted by phone if the study subjects will not see a study doctor on those days.
 
b. Only patients with confirmed high risk features (+ECE and/or + margins) will receive Cisplatin.
 
c. Time of discontinuation is either after last Pembrolizumab dose which will correspond to safety visit at week 20 or at time that patient discontinues treatment due to side effects, progression or withdrawal of consent.
 
d. Safety visit will be completed on week 20 unless study discontinued early at which time it should be done at 30 days post-treatment. 30 day safety follow up visit only needed for subjects who withdraw or discontinue the study.
 
e. Full physical exam only includes full head and neck and fiberoptic exam at week 19 but can be completed between week 11 and 20 to count towards week 19 assessment.
 
f. Pre-operative scans including chest imaging preferably PET/CT and CT neck + contrast. (CT chest and CT neck + contrast would also be acceptable). If contrast contraindicated, MRI of neck is also acceptable. Post CRT imaging requires a PET/CT or CT of neck and chest.
 
g. See procedure manual for tissue specifications and tubes required. MDA fresh tissue to be collected per MDA standard.
 
h. Dental exam to be completed anytime before initiation of radiation.
																		

Trial Period:	Screening Phase		Pre-surgery Dose	Surgery	Adjuvant Treatment										End of Treatment	Post-Treatment		
Treatment Dose Title:	Pre-screening (Visit 1)	Main Study Screening (Visit 2) P	Pre-Surgery Dose P		1	2	3	4	5	6	7	8	9	10	NA	Discon	Safety Follow-up n	Survival Follow-Up a
Scheduling Window (Days):	-35 to -7	-22 to -7	-21 to -7	0	28 to 77	± 1	± 1	± 1	± 1	± 1	± 1	± 3	± 3	± 3	± 14	At time of Discon c	30 days and 3 months post discon	+/- 2 weeks

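### Disease-free status at 1 year (the tested endpoint) and at 3 years can rest on a phone report alone, because no examination or scan is required after about adjuvant week 20 unless relapse is suspected

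*Combined protocol and SAP*

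**What the plan says.** The last required scan is 12 weeks (+/- 2) after radiation, at week 19 of the flow chart (7.1.2.6.2). The full head-and-neck and fiberoptic examination may be done at any time in weeks 11 to 20 (7.1.2.2; 6.1, note e). After that:

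- **Imaging (7.1.2.6.2).** No "further imaging is required after initial assessment unless there is suspicion of relapsed disease".
- **Examination (7.1.2.6.3).** It "should be performed if indicated per standard of care but not required per protocol every 12 weeks for first 2 years", and the same waiver covers the 24-weekly examinations of the next 3 years.
- **Phone contact (7.1.5.4).** Visits are first described as "either in person at a doctor visit or by phone (if being seen by outside oncologist) for the first 2 years". The same paragraph then says "Phone calls are an acceptable form of follow up for all subjects", whether their oncologist is local or outside. Note a of the flow chart gives a third version: "FU visits can be conducted by phone if the study subjects will not see a study doctor on those days".
- **Clinical follow-up.** Section 7.1.2.6.2 says "Patients will be followed clinically for recurrence after initial post-treatment imaging", and 7.1.2.6.3 says "Patients will be followed clinically every three months and any concern for relapsed disease or progression should trigger either imaging or biopsy".

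Section 8.2.2 makes DFS at 1 and 3 years the primary efficacy endpoints and dates a relapse at its discovery. Section 8.2.4.2 compares 1-year DFS with RTOG 9501 (65.4% CRT, 68.8% RT) by a one-sample exact test. Section 8.1.3 sets one-sided alpha at 0.025 with N=40 per stratum, and regards a patient as event-free after at least a year of follow-up without recurrence. No section states what disease assessment is needed for that.

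**The concern.** A phone call establishes survival reliably. Its value for relapse depends on what the patient has noticed or what another physician has found. Without a recent examination or scan, a small mucosal or nodal recurrence, or an asymptomatic distant one, may go unreported.

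A relapse dated at discovery counts against 1-year DFS only if it is found within the year. One that is missed, or found later, counts as a success. There is no concurrent arm followed in the same way, so the error does not cancel; it enters directly into a one-sided comparison with a fixed rate. Since the source of each assessment need not be recorded, the size of the problem could not be established afterwards either.

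**Working it through.** **1. Reproduce the plan's figure.** Inputs: N=40, one-sided alpha 0.025 and targets 86% and 88% (8.1.3); p0 = 0.654 and 0.688 (8.2.4.2). The cut-off r is the smallest count with P(X ≥ r | 40, p0) ≤ 0.025.

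| Stratum | r | P(X ≥ r−1) at p0 | P(X ≥ r) at p0 | Power at target |
|---|---|---|---|---|
| CRT | 33/40 | 0.0339 | 0.0141 | 0.811 |
| RT | 34/40 | 0.0397 | 0.0163 | 0.802 |

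The stated power of over 80% is confirmed in both strata.

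**2. Effect of undetected events.** Let u be the share of true 1-year DFS events not detected by 1 year in this trial, and b the same share in RTOG 9501. The benchmark p0 is an observed rate, so it already contains b. With no drug effect, the DFS observed here is

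1 − (1 − p0)(1 − u)/(1 − b) = 1 − (1 − p0)(1 − m), where m = 1 − (1 − u)/(1 − b).

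So m is the excess share undetected relative to RTOG 9501. If u = b, then m = 0 and the type I error stays at 0.0141 and 0.0163. The documents give neither u nor b, so m is an assumption, shown as a range at unchanged cut-offs:

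| m | CRT observed DFS | CRT type I error | RT observed DFS | RT type I error |
|---|---|---|---|---|
| 0 | 65.4% | 0.014 | 68.8% | 0.016 |
| 5% | 67.1% | 0.024 | 70.4% | 0.027 |
| 10% | 68.9% | 0.040 | 71.9% | 0.042 |
| 20% | 72.3% | 0.100 | 75.0% | 0.097 |
| 30% | 75.8% | 0.213 | 78.2% | 0.199 |

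Example, CRT at m = 10%: 1 − 0.346 × 0.90 = 0.6886, and P(X ≥ 33 | 40, 0.6886) = 0.0404.

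The nominal 0.025 is crossed at m of about 5.3% (CRT) and 4.4% (RT). Expected 1-year events under no effect are 40 × 0.346 = 13.8 and 40 × 0.312 = 12.5, so the crossing corresponds on average to 0.7 and 0.5 excess undetected events. Deaths are DFS events and are presumably found, so the share of *relapses* missed would have to be larger than m.

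**3. How much of the year lies after the last required scan.** Take resection as time zero (an assumption; the plan says treatment allocation). Adjuvant week 1 starts on days 28 to 77, and week 19 is 126 days later: days 154 to 203, or 140 to 217 with the ±14-day window. Under a constant hazard (also an assumption), the share of 1-year events after day d is (p0^(d/365.25) − p0)/(1 − p0). For CRT this is 0.566 at day 140 and 0.356 at day 217; for RT, 0.572 and 0.361. On these assumptions, roughly 36% to 57% of first-year events fall where no scan or examination is required without suspicion.

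**4. The passages side by side.** Within 7.1.5.4, the first sentence ties phone contact to a patient being seen by an outside oncologist; the later sentence removes that condition for everyone. Both cannot govern. Flow-chart note a is closer to the later sentence.

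**The case against.** **The benchmark is an observed rate too.** A reader might infer that DFS here *is* biased upward against RTOG 9501. The documents do not support that. Net bias requires poorer detection here than there, and the surveillance behind 65.4% and 68.8% is nowhere described. This trial's mandatory week-19 scan could even bring early relapse dates forward. For the same reason, the 4%, 10% and 20% figures are not this design's false-positive rates; they hold only for the stated excess m. This objection stands.

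**The 3-year endpoint.** The exact test is specified at 1 year only. Section 8.2.2 calls 3-year DFS primary, while 4.2.3.2 calls it secondary. The ascertainment gap applies at 3 years, but the error rates above do not.

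**Clinical follow-up.** It is tempting to say that phone contact flatly contradicts the promise of clinical follow-up. That term is undefined, and 7.1.2.6.3 waives the examination in the same paragraph, so the two sit uneasily rather than contradict. The firm contradiction is the one inside 7.1.5.4.

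**Safeguards exist.** Any concern should trigger imaging or biopsy (7.1.2.6.3), suspected relapse should be confirmed (7.1.5.4), deaths count (8.2.2), and a call can collect findings from ongoing care. These make a large m less likely. But the first two act only once relapse is suspected, and nothing requires that findings from outside care be obtained.

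**Conclusion.** The gap is a stated rule, not missing detail: after about week 20, disease-free status at 1 and 3 years may rest on a phone report alone, and 7.1.5.4 gives two incompatible rules for when phone contact is allowed. Missed or late-found relapses can only raise observed DFS, so the 1-year comparison can be biased in the favourable direction, by an unknown amount. Whether it is biased relative to RTOG 9501 depends on that trial's surveillance.

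The test has little slack. An excess of about 5% of 1-year events undetected takes the type I error to about the nominal 0.025, and 10% takes it to about 0.04 in both strata. These figures assume N=40 per stratum, no drug effect and the stated m. This is a cheap improvement worth making, not evidence that the endpoint is invalid.

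**What to change.** 1. Reconcile 7.1.5.4, 7.1.2.6.2, 7.1.2.6.3 and flow-chart note a, so that a phone contact used for DFS is backed by a retrieved routine-care record, from the study or an outside physician, of a dated examination or scan.
2. Record in the CRF the date and source of each disease assessment: examination, imaging or phone.
3. In 8.2.4.2, state which assessment, within what window around 1 and 3 years, is needed to count a patient as disease free. In the binary analysis, count a relapse found at that landmark assessment as an event at the landmark. Otherwise a relapse discovered just after 12 months is dated after the landmark and still scores as a 1-year success.
4. Report how many 1-year successes rest on phone contact only. Add a sensitivity analysis that censors at the last adequate disease assessment (Kaplan-Meier) and does not count phone-only patients as successes (exact test).

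No new procedure is required. Because 7.1.2.6.3 asks for the examination only if indicated, some patients will have no record near the landmark; item 4 covers them. N, cut-offs and stated power are unchanged for the main test. The cost is a small amendment, a source-and-date entry in the CRF, staff time to retrieve records, and possibly a less favourable or less precise DFS estimate.
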